#### Sample size:

Consistent with the descriptive nature of this study, our intention is to capture as many TEEs as possible within those performed across the clinical indications of interest for this study. Based on

prior research and Quality Assurance data, over the period of one year, we estimate a total of approximately 100 studies to be performed and analyzed as part of this study.

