# **Overall objectives**

The primary objective of this study is to determine the **clinical impact** and **safety** of transesophageal echocardiography (TEE) performed during the evaluation of critically-ill patients in the **emergency department** and **intensive care settings**.

The secondary objective(s) of this study are to **characterize the use of this imaging modality** in the subsets of critically-ill patients in **shock and cardiac arrest**; including but not limited to; description of the frequency of studies, clinical indications, clinician characteristics, echocardiography findings, timing of studies, procedure-related complications and patient outcomes.

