# **Study Design**

### Design

We plan to conduct a prospective observational study involving a convenient sample of patients receiving a TEE as part of their clinical care in emergency department (ED) and intensive care unit (ICU) settings. The study will enroll adult patients receiving focused TEE as part of their routine care for the most common clinical indications of focused TEE in critical care patients in ED and ICU settings including: 1. Evaluation of intra-arrest and post cardiac arrest in inhospital (IHCA) and out-of-hospital cardiac arrest (OHCA), 2. Evaluation of patients in shock, 3. Hemodynamic monitoring, and 4. Procedural guidance.

Data will be collected from the patients' electronic medical record (EMR) and EMS run-sheets in the case of OHCA cases. Transesophageal echocardiography (TEE) images routinely recorded for quality assurance and as part of standard clinical care, will be collected. Patients will be

enrolled in the study by clinicians participating from their care who are involved in the performance of TEE. Following identification of eligibility criteria by the enrolling clinician, a RedCap data collection instrument will be used to prospectively gather basic demographics, and clinical data, including the indication for the TEE (i.e. including intra-arrest or post arrest, evaluation of shock, hemodynamic monitoring or procedural guidance), operator findings on the TEE, probe insertion procedure details, TEE views obtained during the study, clinician's interpretation of the images, change in management (if any) as a result of the information provided by TEE. Procedure-related immediate complications, and outcomes when indicated.

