Minimal patient demographic information to be collected including: age, gender, and BMI. In the case of cardiac arrests, when applicable the following information will be collected: if the arrest was witnessed, location of arrest, if bystander CPR was performed, will be obtained from the EMR and EMS run sheets. Identification of certain disease states in the medical history patients such as coronary artery disease, congestive heart failure, chronic kidney disease, diabetes mellitus, hypertension, previous STEMI, ventricular assist device, and implantable cardioverterdefibrillator will also be obtained from the EMR and prospectively entered to the RedCap data form. For cases of OHCA, data collection will also include an analysis of pre-hospital care to examine the following factors (Ustein Cardiac Arrest Variables); estimated time of arrest, response time, EMS interventions (chest compressions, defibrillation, airway procedures, dosing and timing of drug administration). For all cardiac arrest cases, information collected will also include time of arrest, ED arrival time in case of OHCA, time to first image of TEE, time of first rhythm, and times and type of intervention (mechanical CPR, arterial line, epi administration, etc.) The study of patient outcomes will be specific to the clinical indication and will include ROSC, survival to hospitalization and discharge in OHCA. In cardiac arrest cases, additional factors pertaining CPR physiology will be examined.

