#### **Analysis Plan**

Baseline and demographic characteristics will be summarized by standard descriptive statistics (including mean and standard deviation for continuous variables such as age and standard percentages for categorical variables such as gender). Continuous variables will be analyzed using Student's t-test, categorical data using Chi-square. Descriptive statistics will be presented as a mean with standard deviation, or as a median with an interquartile range. Differences in patient characteristics will be analyzed using  $\chi^2$  testing, Student's t-test, or the Mann-Whitney U test, as appropriate. We will provide frequencies with their binomial 95% confidence intervals for descriptive purposes. For bivariate or multivariable analyses, we will use logistic regression, ANOVA, or chi-squared testing, as appropriate. Statistical methods will be performed in statistical software (STATA).

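### Do the planned intervals come out too narrow because the protocol enrols patients, counts TEEs and has no rule for repeat scans?

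*Protocol*

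**What the plan says.** Under Study Design, the Protocol describes a sample of patients: "The study will enroll adult patients receiving focused TEE as part of their routine care". The data collection form records, among other items, "the indication for the TEE (i.e. including intra-arrest or post arrest, evaluation of shock, hemodynamic monitoring or procedural guidance". Outcomes are described per patient: "The study of patient outcomes will be specific to the clinical indication and will include ROSC, survival to hospitalization and discharge in OHCA".

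The Sample size section counts examinations. It says "our intention is to capture as many TEEs as possible" and then "we estimate a total of approximately 100 studies to be performed and analyzed as part of this study". No expected number of patients is given. The secondary objectives put both levels in one list: "description of the frequency of studies, clinical indications, clinician characteristics, echocardiography findings, timing of studies, procedure-related complications and patient outcomes".

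On methods, the Analysis Plan says "We will provide frequencies with their binomial 95% confidence intervals for descriptive purposes" and "For bivariate or multivariable analyses, we will use logistic regression, ANOVA, or chi-squared testing, as appropriate", alongside t-tests, chi-square and Mann-Whitney tests. It names no clustered or repeated-measures form. No section limits a patient to one TEE, designates an index TEE, or says how a second one would be handled.

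**The concern.** Enrolment is by patient, the expected size is in TEEs, and the named methods, in their ordinary form, treat records as independent. A second TEE in the same patient is plausible from the listed indications: a scan during arrest could be followed by one after arrest, and monitoring or procedural guidance could prompt another. An aim of capturing as many examinations as possible would tend to bring such scans in.

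If each scan became its own record, two records from one patient would carry less information than two records from different patients. Binomial intervals and logistic models would then look more precise than they are. This would touch the primary objective, clinical impact and safety. A reader might also be unable to tell whether a complication rate is per scan or per patient.

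**Working it through.** **Inputs.** From the Protocol: about 100 TEEs (Sample size) and 95% binomial intervals (Analysis Plan). Not in the Protocol, and so assumed: the number of patients behind the 100 TEEs, and the ICC between scans of the same patient.

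**The Protocol's own figure.** The 100 is a feasibility count from prior research and quality assurance data. It has no power, effect size or precision target, so there is no calculation to reproduce and none to correct.

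**Precision with 100 independent records.** At a proportion of 50%, the half-width is 1.96 × √(0.25/100) = 0.098, or 9.8 points.

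**Effect of repeats.** With m scans per patient:

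- design effect (DEFF) = 1 + (Σm²/Σm − 1) × ICC
- narrowing factor = √DEFF
- correct half-width = 9.8 × factor
- actual coverage of the naive 95% interval = 2Φ(1.96/factor) − 1

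Example: 91 patients, 9 scanned twice. Σm = 82 + 18 = 100 and Σm² = 82 + 36 = 118, so Σm²/Σm = 1.18. At ICC 0.5, DEFF = 1 + 0.18 × 0.5 = 1.09, the factor is 1.044 and the half-width is 9.8 × 1.044 = 10.2. At ICC 1, DEFF = 1.18, the factor is 1.086 and the half-width is 9.8 × 1.086 = 10.6.

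| Patients (scanned twice) | Σm²/Σm | ICC | DEFF | Factor | Half-width at 50% (points) | Coverage of naive interval |
|---|---|---|---|---|---|---|
| 100 (0) | 1.00 | any | 1.00 | 1.00 | 9.8 | 95.0% |
| 91 (9) | 1.18 | 0.2 | 1.036 | 1.018 | 10.0 | 94.6% |
| 91 (9) | 1.18 | 0.5 | 1.09 | 1.044 | 10.2 | 94.0% |
| 91 (9) | 1.18 | 1 | 1.18 | 1.086 | 10.6 | 92.9% |
| 80 (20) | 1.40 | 0.2 | 1.08 | 1.039 | 10.2 | 94.1% |
| 80 (20) | 1.40 | 0.5 | 1.20 | 1.095 | 10.7 | 92.6% |
| 80 (20) | 1.40 | 1 | 1.40 | 1.183 | 11.6 | 90.2% |
| 50 (50) | 2.00 | 0.5 | 1.50 | 1.225 | 12.0 | 89.1% |
| 50 (50) | 2.00 | 1 | 2.00 | 1.414 | 13.9 | 83.4% |

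The last two rows are an outer bound; nothing in the Protocol suggests that every patient is scanned twice. An ICC of 1 is exact for a patient outcome copied onto every record. It is extreme for findings, management changes or complications, which can differ between scans.

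**Zero complications.** The exact upper 95% limit is 1 − 0.025^(1/n): 3.6% for n = 100, 4.0% for 91, 4.5% for 80 and 7.1% for 50. The first is a limit on risk per examination and the others are limits on risk per patient. These are different quantities, so the gap between them does not show that the first interval is too narrow. For procedure-related complications, a per-examination denominator is legitimate.

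**Do the texts contradict each other?** Study Design speaks of patients receiving a TEE and of a form that captures the indication for the TEE, in the singular, once eligibility is established. Read that way, each enrolled patient gives one record, and about 100 studies means about 100 patients. The Sample size wording also allows more than one scan per patient. The passages leave the matter open, but they do not conflict.

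**The case for a change.** The strongest case for a change is that this is more than missing detail. The Protocol itself sets the count in TEEs, enrolment in patients and the methods in their ordinary form, and the primary objective is affected. A remedy would be cheap: name the unit for each outcome and cluster by patient where scans repeat. It would also need a patient key on each record. The Protocol specifies none, and Subject Confidentiality says identifiers are removed where feasible.

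Part of this stands. The unit is not stated, and per-scan and per-patient complication rates do need to be told apart in the report. The rest does not require an amendment. The Analysis Plan names broad families of methods and leaves the choice to what is appropriate; a logistic model with patient-clustered standard errors is still logistic regression, and Stata provides it as an option. This argument is weaker for the plain binomial interval, which has no clustered form under that name. On linkage, removing identifiers does not rule out a coded study number, and the Procedures section has the data entered from patient charts, where a second scan of the same patient would be visible.

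The stated mortality of about 90% (Potential Study Risks) may make repeats less common. It does not exclude two scans before death, so it gives only modest support.

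**Conclusion.** No change to the plan is needed. The observation is accurate: patients are enrolled, TEEs are counted and no rule covers repeats. Harm follows only if repeats occur and are then analysed as independent records, and the Protocol states neither. What remains is an unwritten unit-of-analysis rule of the kind a statistical analysis plan usually sets. A competent analyst would fill it by counting patient outcomes once per patient and allowing for clustering in scan-level results if there are repeats.

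If the gap were filled badly, the size depends on assumed values. With 9 of 91 patients scanned twice, intervals would be too narrow by a factor of 1.04 (ICC 0.5) to 1.09 (ICC 1), or 0.4 to 0.8 points on a half-width of 9.8. With 20 of 80 scanned twice, the factor is 1.10 to 1.18. With no repeats there is no effect. In a descriptive convenience sample with no power or precision target, the milder case would not alter any conclusion. The larger cases rest on repeat rates for which the Protocol gives no basis.

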## **Subject Confidentiality**

The long-range plan for protecting the confidentiality of research data, including a schedule for destruction of identifiers associated with the data.

Paper-based records will be kept in a secure location and only be accessible to personnel involved in the study.

Computer-based files will only be made available to personnel involved in the study through the use of access privileges and passwords.

Prior to access to any study-related information, personnel will be required to sign statements agreeing to protect the security and confidentiality of identifiable information.

Wherever feasible, identifiers will be removed from study-related information.

A waiver of documentation of consent is being requested, because the only link between the subject and the study would be the consent document and the primary risk is a breach of confidentiality. (This is not an option for FDA-regulated research.)

Precautions are in place to ensure the data is secure by using passwords and encryption, because the research involves web-based surveys.

REDCap, as an encrypted program, will be used to store all study variables and extracted data points.

# **Sensitive Research Information\***

No

### **Data Disclosure**

### **Protected Health Information/Data Protection\***

### **Consent Process**

Not Applicable

#### **Potential Study Risks**

Given the design as an observational protocol, there are no interventions as part of this study. As explained before, all the interventions such as procedures occurring during this protocol are the standard clinical practice and their use will be directed by the treating physicians as part of the standard care.

Radioisotopes/radiation-producing machines (e.g., X-rays, CT scans, fluoroscopy) and associated risks: No radioisotopes or radiation-producing machines will be used during the protocol.

Physical well-being: Participation in this study will not incur any additional risk to subjects' physical well being beyond what would be experienced during standard care. Psychological well-being: Participation in this study will not incur any additional risk to subjects' psychological well being beyond what would be experienced during standard care. Economic well-being. Participation in this study will not incur any additional risk to subjects' economic well being beyond what would be experienced during standard care. Social well-being. Participation in this study will not incur any additional risk to subjects' economic well being beyond what would be experienced during standard care. Social well-being. Participation in this study will not incur any additional risk to subjects' social well being beyond what would be experienced during standard care. Social well being beyond what would be experienced during standard care. Social well being beyond what would be experienced during standard care. Social well being beyond what would be experienced during standard care. Although the risk of mortality in our patient population is high (approximately 90%), the risk of the observations made in this study are minimal as all observations are currently being recorded as part of standard of care. All laptops, desktops, and mobile devices used to access, transmit, or store Prohibited or Restricted Data as defined under the Data Classification Guidelines are encrypted. We will make sure that any new device used in this study will be encrypted prior to use.

#### **Potential Study Benefits**

There will be no direct benefit to patients enrolled in this study. However, the knowledge gained from this research and specifically the greater understanding on the clinical impact and potential to improve outcomes of TEE in the care of critically-ill patients, will contribute greatly to the field and society at large.

Among other applications, this knowledge may contribute to the creation of guidelines for physicians that use this emerging ultrasound modality when caring for critically-ill patients, and may ultimately save patients from death and other adverse outcomes. The medical community's increased understanding of the value of this imaging modality and best practices in its use for patients with specific clinical conditions such as shock and cardiac arrest is also likely to result from this study.

#### **Risk / Benefit Assessment**

Minimal Risk
